4.2 Masking and Unmasking

4.2.1 MASKING

During the vehicle run-in period, the subject will be masked. During the randomized study intervention period, the Investigator and site staff performing eligibility/efficacy and safety assessments and the subjects will be masked. Subjects will remain masked during the randomized phase. Subjects will be informed that they all will receive vehicle at some point in the study, but the exact timing will not be specified. AR-15512 (0.003%) and AR-15512 vehicle will be provided in identical single-use blow-fill-seal containers.

4.2.2 UNMASKING

A randomization schedule for allocating the study interventions within a site will be prepared by an unmasked statistician who is not involved in the day-to-day conduct of the study.

Study intervention assignments will be masked to the Investigator, the clinical study team (Sponsor, personnel involved in day-to-day study management, Monitors, Data Managers, and Statisticians), and the subjects. Only in case of medical emergency or occurrence of AEs that warrant unmasking in the opinion of the Investigator, will the study intervention assignment(s) be unmasked and made available to the

Investigator and the Medical Monitor. In the absence of medical need, the randomization code will not be available to the above personnel until after the study is completed and the database is locked.

If the Investigator feels it is necessary to unmask a subject's study intervention assignment after an emergency situation, the Investigator should contact the Medical Monitor or designee. Only after consultation with the Medical Monitor will a decision be made as to whether or not the study intervention for the subject should be unmasked. The study intervention assignment will be revealed on a subject-by-subject basis, thus leaving the masking on the remaining subjects intact.

5. Sample Size and Power Considerations

Two hundred two (202) ITT population subjects (study eyes) per treatment group yields 99% power to conclude superiority of 0.003% AR-15512 over vehicle in the proportion of subjects with ≥ 10 mm increase in unanesthetized Schirmer score on Day 14, assuming a true difference of proportions (AR-15512 vs vehicle) of 80% vs 30% and a two-sided alpha=0.05.

Additionally, 202 ITT population subjects (study eyes) per treatment group yields 99% power to conclude superiority of 0.003% AR-15512 over vehicle in the mean change from baseline in SANDE score on Day 28 assuming a true difference (AR-15512 minus vehicle) of -7.9, a common standard deviation (SD) of 17.72, and a two-sided alpha=0.05.

Accounting for subject discontinuations, approximately 460 total subjects (230 per treatment arm) will be randomized assuming a dropout rate of 10%.

6. Data Preparation

6.1 Input Data

Study data will primarily be recorded on the electronic Case Report Forms (eCRFs) supplied by Statistics & Data Corporation (SDC) using electronic data capture (EDC) system, Medidata RAVE. In addition, the following study data which is not captured directly within the EDC system but is obtained from external vendors will also be included for analysis. These data sources are described in detail in data transfer agreements developed between data management and the respective external laboratory:

- Central laboratory data from ACM Global Laboratories (hematology, chemistry, and urinalysis)

When all prerequisites for database lock have been met, including availability of all masked external data, the database will be locked. Following database lock, approval will be obtained from the Sponsor to unmask the study. Any changes to the database after data have been locked can only be made with the approval of the Sponsor in consultation with SDC.

Final analysis will be carried out after the following have occurred:

- Database lock has occurred, including receipt of all final versions of external vendor data, with written authorization provided by appropriate SDC and Sponsor personnel.
- Protocol deviations have been identified and status defined (major/minor deviations).
- Analysis populations have been determined.
- Randomized treatment codes have been unmasked.

6.2 Output Data

Data from EDC and external data will be transferred to SDC Biostatistics and incorporated into standard formats following the Study Data Tabulation Model (SDTM). Data will then be mapped to analysis datasets using the Analysis Data Model (ADaM). Both SDTM- and ADaM-formatted data will be used to create the subject listings, while all tables and figures will be based on the ADaM-formatted data. The SDTM and ADaM model versions, implementation guide versions, Pinnacle 21 version will be documented in the respective reviewer's guides in the final CDISC package. Define.xml will be created for SDTM and ADaM using the Define-XML version 2.0 model or above.

7. Analysis Populations

7.1 Intent-to-Treat

The Intent-to-Treat (ITT) population includes all randomized subjects. The primary efficacy analysis will be performed on the ITT population. Subjects in the ITT will be analyzed as randomized.

7.2 Per Protocol

The Per Protocol (PP) population includes subjects in the ITT population who do not have significant protocol deviations likely to seriously affect the primary outcome of the study and who complete the trial through Day 28. Protocol deviations will be assessed prior to database lock and unmasking. The PP population will be analyzed using observed data only for efficacy variables. Subjects in the PP population will be analyzed as treated.

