9.4 Missing Data

The primary analysis will be completed with available data per subject as specified in Estimand 1 from the intent-to-treat (ITT) population, assuming the overall study discontinuation rate is <5% in each arm. If the study discontinuation rate is $\geq 5\%$ in each arm then the primary analysis will be based on multiple imputation methodology as specified in Estimand 2, and the available data analyses will become robustness analyses.

Additional robustness analyses will include repeating the primary analysis on the ITT population imputing missing data as failures for the proportion of subjects with ≥ 10 mm increase in unanesthetized Schirmer score on Day 14 endpoint; using multiple imputation methodology under different assumptions of missingness (at random and not at random) each using 30 imputed values; the ITT population imputing missing data using last observation carried forward (LOCF); the ITT population using trimmed means; and the per-protocol (PP) population with available data per subject.

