9.8.2 Per Protocol Population

The per protocol (PP) population includes subjects in the ITT population who do not have significant protocol deviations likely to seriously affect the primary outcome of the study and who complete the trial through Day 90. Protocol deviations will be assessed prior to database lock and unmasking. The PP population will be analyzed using observed data only for efficacy variables. Subjects in the PP population will be analyzed as treated.

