The purpose of this statistical analysis plan (SAP) is to describe in detail the planned analyses and reporting for protocol AR-15512-CS302, Amendment 2 (Rev 2) dated 04MAY2023. The statistical analysis methods presented in this document will supersede the statistical analysis methods described in the clinical protocol. If additional analyses are required to supplement the planned analyses described in this SAP, they may be completed and will be identified in the clinical study report.

This SAP is being written with due consideration of the recommendations outlined in the most recent International Conference on Harmonisation (ICH) E9 Guideline entitled Guidance for Industry: Statistical Principles for Clinical Trials¹, the most recent ICH E9 (R1) Guideline entitled Guidance for Industry: Statistical Principles for Clinical Trials: Addendum: Estimands and Sensitivity Analysis in Clinical Trials², and the most recent ICH E3 Guideline entitled Guidance for Industry: Structure and Content of Clinical Study Reports³.

2. Study Objectives

To evaluate the safety and efficacy of topical ophthalmic 0.003% AR-15512 compared to its vehicle administered twice daily (BID) in subjects with dry eye disease (DED).

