2.1.1 PRIMARY ENDPOINT

- Proportion of subjects with ≥ 10 mm increase (post-drop on Day 14 vs pre-drop at Baseline) in unanesthetized Schirmer score on Day 14

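### The SAP's per-protocol set requires completion to Day 28 although the primary endpoint is read on Day 14, so it drops a few subjects for exiting after their outcome was measured

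*SAP*

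**What the plan says.** SAP 2.1.1 defines the primary endpoint as the proportion of subjects with at least a 10 mm "increase (post-drop on Day 14 vs pre-drop at Baseline) in unanesthetized Schirmer score on Day 14". Nothing measured after Day 14 enters it.

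SAP 7.2 builds the PP set from ITT subjects under two conditions. The first is the absence of significant deviations likely to seriously affect the primary outcome. The second is completion of the trial to a fixed day. The wording joins them, so the set holds only subjects who meet the first and "who complete the trial through Day 28". The set is analysed with observed data only. SAP section 9 says that the number of subjects in it will be reported.

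Protocol 9.8.2 has the same sentence with a later day: "primary outcome of the study and who complete the trial through Day 90". SAP section 1 settles which applies: "The statistical analysis methods presented in this document will supersede the statistical analysis methods described in the clinical protocol". Day 28 is therefore the operative cut-off.

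The primary efficacy analysis is on the ITT population (SAP 7.1 and 13.4). Protocol 9.4 lists, among the robustness analyses of the primary, "the per-protocol (PP) population with available data per subject".

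**The concern.** The two conditions do not serve the same purpose. The deviation clause is tied to the primary outcome. The completion clause is not, because it reaches two weeks past it. Someone who dosed correctly, had a valid Day 14 Schirmer test and left on Day 20 has a complete primary outcome and no deviation that could have affected it, yet is excluded.

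That is selection on a post-outcome event. It matters if leaving is related to how the subject responded. The SAP treats this as possible: Estimand 1 (SAP 2.3.1) handles withdrawal for lack of efficacy, adverse events or disallowed treatment as missing not at random, and lack of efficacy and adverse events are among the discontinuation reasons in SAP section 9. If non-responders are more likely to leave, the PP responder rate rises. ITT and PP results could then differ, or agree, for reasons unrelated to adherence up to Day 14, and adherence is what a PP comparison is meant to probe. The two secondary endpoints read on Day 1 and the Schirmer change on Day 14 (SAP 2.1.2) are affected in the same way.

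**Working it through.** **Inputs.** Randomized: 460, 230 per arm. Dropout: 10%. Responder rates: 80% vs 30%. Sample-size basis: 202 per arm, two-sided alpha 0.05 (all SAP section 5). Expected Day 90 completers: 414 (Protocol 4.1). PP cut-off: Day 28 (SAP 7.2). Primary visit: Day 14 (SAP 2.1.1).

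**Plan's own figures.**
- Completers: 460 × (1 − 0.10) = 414, as stated.
- Power: z = 0.50 / √[(0.8×0.2 + 0.3×0.7)/202] − 1.96 = 0.50/0.0428 − 1.96 ≈ 9.7, so power exceeds 0.999. This is consistent with the stated 99%.

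**How many subjects the rule removes.** The documents do not say when dropouts occur. Assume that they are spread evenly over 90 days.
- Exits between Day 14 and Day 28: N × d × (28 − 14)/90.
- d = 10%: 460 × 0.10 × 14/90 = 7.2, or 1.6% of those randomized.
- d = 5%: 3.6. d = 15%: 10.7 (11.2 with a constant hazard). The range is about 4 to 11.
- At 10%, subjects eligible before deviations are applied: about 453 if only Day 14 is required (460 − 7.2), and about 446 under the Day 28 rule (453 − 7.2).
- Without any timing assumption, the only bounds at 10% dropout are 0 and 46 (460 × 0.10).

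**How far the PP result could move.** Seven subjects are 3.6 per arm; round up to 4. Expected responders are 0.80 × 230 = 184 (active) and 0.30 × 230 = 69 (vehicle). For simplicity, the few exits before Day 14 are ignored.

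| Who leaves between Day 14 and Day 28 | Active | Vehicle | Difference | Shift |
|---|---|---|---|---|
| Unrelated to response | 80.0% | 30.0% | 50.0 | 0 |
| 1.6% per arm; active leavers respond at 50%, vehicle leavers at 30% | (0.80 − 0.016×0.50)/0.984 = 80.5% | 30.0% | 50.5 | +0.5 |
| 4 non-responders in each arm | 184/226 = 81.4% | 69/226 = 30.5% | 50.9 | +0.9 |
| 4 non-responders in the active arm only | 184/226 = 81.4% | 69/230 = 30.0% | 51.4 | +1.4 |

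The last two rows are extreme, because every leaver is taken as a non-responder although only 20% of active subjects are expected to be. The direction is not fixed either: four active responders leaving would give 180/226 = 79.6%, a shift of −0.4 points in that arm.

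**Power.** The ITT analysis does not use the PP definition, so its power does not change. Even within the PP set, at about 223 per arm (446/2) before deviations, power for 80% vs 30% exceeds 0.999.

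**The case against.** The strongest reply is that Day 28 is a coherent choice. SAP 7.2 defines one PP set for efficacy variables generally, and Day 28 is the visit of the first-listed secondary endpoint, SANDE, which is also the second endpoint used to justify the sample size. A common set reaching the later of the two powered endpoints keeps the same subjects in both comparisons. The documents do not give this reason, but it is plausible. It explains the cut-off without making it suitable for an outcome already complete at Day 14.

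Three further points stand and limit the finding. First, no observed Day 14 value is lost from the primary analysis: the subject who leaves on Day 20 contributes that value to the ITT comparison. Second, nothing in the documents links Day 14 Schirmer response to exit before Day 28, so differential exit is a possibility and not an expectation. Third, the role of the PP analysis as a check on the primary is visible only in Protocol 9.4. The visible SAP analysis sections name no PP efficacy analysis, but the SAP has redacted gaps, so neither its absence nor its exact use can be inferred.

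A reader might also take the protocol's Day 90 rule and infer a much larger problem. On the same even-dropout assumption, 460 × 0.10 × 76/90 ≈ 39 subjects with Day 14 data would be excluded. If 19 active non-responders were removed, the active rate would become 184/211 = 87.2%, or +7.2 points. The documents do not support that as the planned analysis, because the SAP's methods supersede the protocol's and the SAP says Day 28.

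**Conclusion.** The point holds in a limited form. The operative PP definition selects on retention after the primary outcome, and neither the SAP's precedence over the protocol nor the Day 28 SANDE endpoint justifies that for a Day 14 measure. The practical size is small: about 7 of 460 subjects, and at most about 1 point on a planned difference of 50 if both arms lose only non-responders (1.4 if only the active arm does). These figures rest on 10% dropout spread evenly over 90 days and on an extreme assumption about who leaves. The bias is zero if exit after Day 14 is independent of response.

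It would be wrong to infer that the trial's conclusion is at risk. The primary inference is on the ITT population, and nothing here touches it or its power. This is a cheap improvement to a supportive analysis, of low severity.

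**What to change.** Revise SAP 7.2 before unmasking so that PP membership is defined by endpoint: ITT subjects with a valid baseline and a valid assessment at the endpoint's visit, and no significant deviation up to that visit likely to affect that endpoint. For the primary endpoint and the Schirmer change on Day 14, the visit is Day 14. For Day 1, Day 28 and Day 90 endpoints it is the corresponding visit.

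Aligning Protocol 9.8.2, which still says Day 90, is optional because the SAP governs; it would only remove a conflicting definition from the file.

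The cost is a few lines of SAP text and a visit-specific PP flag in the analysis dataset, set at the deviation review already planned before database lock and unmasking. The downside is that the PP sample size will differ by endpoint, so each PP table must state its own n.

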7.3 Safety

The Safety population includes all randomized subjects who have received at least one dose of the investigational product. The Safety population will be analyzed for all safety assessments. Subjects in the Safety population will be analyzed as treated.

8. General Statistical Considerations

8.1 Unit of Analysis

Safety endpoints will be analyzed for both eyes. For efficacy endpoints assessed at the eye level, the unit of analysis will be the “study eye” as defined in [Section 8.2](#). For efficacy endpoints assessed in both eyes (OU), the unit of analysis will be the subject.

8.2 Study Eye Selection

[figure not shown]
The study subject must have at least one eye (the same eye) meeting all the inclusion criteria and none of the exclusion criteria at both Screening and Baseline (Day 1) visits where applicable. Study subjects will be dosed in both eyes. If both eyes are eligible at the time of randomization, the study eye will be defined as the eye with the lower pre-drop unanesthetized Schirmer score at the Baseline (Day 1) visit. If both eyes still qualify and have the same pre-drop unanesthetized Schirmer score, the right eye (OD) will be designated as the study eye.

Study eye will not be directly collected in EDC. Instead “Qualifying Eye” will be collected at Baseline (Day 1) visit. When one eye is the qualifying eye, then it will be the study eye. If both eyes are qualified, then study eye will be derived programmatically based on study eye selection criteria in this section. The non-study eye will be referred to as the fellow eye.

8.3 Missing or Inconclusive Data Handling

8.3.1 MISSING EFFICACY ASSESSMENTS

The primary analysis will be based on multiple imputation (MI) methodology as specified in Estimand 1 ([Section 2.3.1](#))

8.4 Definition of Baseline

Baseline is defined as the last non-missing measure prior to the initiation of randomized study intervention.

- The efficacy endpoint baseline will be the Baseline (Day 1) measurement. Screening visit and unscheduled visit measurements if any prior to the initiation of randomized study intervention **will not be considered** for baseline even when Baseline (Day 1) measurement is missing.
- For unanesthetized Schirmer test measures taken at both pre-drop and post-drop, the pre-drop measure at Baseline (Day 1) will be the baseline for primary and secondary analyses as specified

in Section 2.1.1 and Section 2.1.2, [REDACTED]
[REDACTED]

- The safety endpoint baseline will be the last non-missing measurement prior to the initiation of randomized study intervention.

8.5 Data Analysis Conventions

All data analysis will be performed by SDC. Statistical programming and analyses will be performed using SAS® Version 9.4 or higher. Output will be provided in rich text format (RTF) for tables and portable document format (PDF) for tables, listings, and figures using landscape orientation.

Summaries for continuous and ordinal variables will include the number of observations (n), arithmetic mean, SD, median, minimum, and maximum. Minima and maxima will be reported with the same precision as the raw values; means and medians will be presented to one additional decimal place than reported in the raw values. Standard deviations will be presented to two additional decimal places than reported in the raw values. Summaries for discrete variables will include counts and percentages. All percentages will be rounded to one decimal place (i.e., XX.X%). Change from baseline will be calculated as, Post-Baseline Result – Baseline, and treatment comparisons will be calculated as, 0.003% AR-15512 – Vehicle.

All statistical tests will be two-sided with a significance level of 0.05 ($\alpha=0.05$) unless otherwise specified. Confidence intervals (CIs) for differences between treatment groups will be two-sided at 95% confidence. All p-values will be rounded to 4 decimal places; p-values less than 0.0001 will be presented as “<0.0001”; p-values greater than 0.9999 will be presented as “>0.9999”. All odds ratios or 95% CI values less than 0.001 will be presented as “<0.001,” and values greater than 999.999 will be presented as “>999.999.”

Unless otherwise specified, summaries will be presented by treatment group and, where appropriate, visit. Listings will be presented by treatment group, subject number, visit/time point, and parameter as applicable using all randomized subjects. Early termination visit (ET) and unscheduled visits will not be summarized in table summaries and will only be presented in listings.

[REDACTED]

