3.2 Schedule of Visits and Procedures

The Schedule of Visits and Procedures is shown in Table 1.

Table 1 Schedule of Visits and Procedures

	Start of 2 Week Run-In (AR-15512 Vehicle)	Randomized Study Intervention Period (BID-OU, 1:1 Randomization 0.003% AR-15512: AR-15512 Vehicle)						
		Screening (Day -14)	Baseline (Day 1)	Day 7	Day 14	Day 28	Day 60	Day 90 (Study Exit)
Visit ¹	Screening (Day -14)	Baseline (Day 1)	Day 7	Day 14	Day 28	Day 60	Day 90 (Study Exit)	Early Termination
Visit Window (Days)	+3 ²	N/A	±2	±2	±2	±5	-2/+5	N/A
Informed consent	X							
Demographics	X							
Collection of used / unused study intervention		X		X	X	X	X	X
Medical, ophthalmic, and surgical history	X							
Prior or concomitant medication review	X	X	X	X	X		X	X
AE review	X	X	X	X	X		X	X
Vital signs (heart rate and blood pressure)	X	X					X	X
Urine pregnancy test (WOCBP only)	X	X					X	X
Symptom questionnaire (VAS) (Ocular Discomfort, Eye Dryness)	X	X	X	X	X		X	
SANDE questionnaire (VAS)	X	X	X	X	X		X	
Corrected visual acuity	X	X	X	X	X		X	X
Slit-lamp biomicroscopy	X	X	X	X	X		X	X

		Start of 2 Week Run-In (AR-15512 Vehicle)	Randomized Study Intervention Period (BID-OU, 1:1 Randomization 0.003% AR-15512: AR-15512 Vehicle)					
Visit ¹	Screening (Day -14)	Baseline (Day 1)	Day 7	Day 14	Day 28	Day 60 ⁶	Day 90 (Study Exit)	Early Termination
At least 10-minute rest period	X	X	X	X	X		X	
CAE exposure	X							
Inclusion and exclusion criteria	X	X						
Randomization		X						
Dispensing of study intervention ⁴	X	X		X	X	X		
At least 30 and up to 45-minute rest period		X	X	X	X		X	
Pre-drop unanesthetized Schirmer test		X	X	X	X		X	
At least 15 and up to 20-minute rest period		X	X	X	X		X	
In office administration of study intervention ⁵	X	X	X	X	X		X	
Post-drop unanesthetized Schirmer test		X	X	X	X		X	
Hematology, chemistry, and urinalysis		X					X	X
Intraocular pressure	X	X					X	X
Dilated fundus exam	X	X					X	X
Study exit							X	X

¹ All office visits must be arranged at approximately the same time of day \pm 1 hour.

² The Baseline visit should be scheduled between 11 and 14 days after the Screening visit. If absolutely necessary, the Baseline visit may be delayed up to 7 days (extending the run-in period to a maximum of 21 days).

³ Administered every 5 minutes while in the CAE.

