12.1 Dosing Compliance

At the Screening visit, the morning dose will be administered in clinic by the subject under supervision from site personnel. For the Baseline (Day 1), Day 7, Day 14, Day 28, and Day 90 visits, the “evening” dose will be administered by designated site personnel; all other doses will be administered by the subject. Study intervention compliance will be assessed by site records for these treatments.

The subjects' used and unused study intervention vials will be collected on the Treatment Kit Accountability Log eCRF page from the Baseline (Day 1) visit up to and including the Day 90 (or Early Termination [ET]) to assess dosing compliance. If the subject's compliance between visits is less than 80% or more than 125% based on the expected number of used and unused vials, then the subject will be deemed non-compliant, and a protocol deviation must be recorded. The study centers will keep an accurate accountability record that specifies the amount of study intervention dispensed to each subject, the amount of study intervention returned to the site, and the dates of each.

Overall study intervention dosing compliance (% compliance) starting from Baseline (Day 1) to Day 90 (or ET) will be assessed by:

$$\text{Compliance (\%)} = \frac{\text{Number of Actual Doses Received}}{\text{Number of Expected Doses}} \times 100$$

The number of actual doses received is calculated as the following:

$$(\text{sum of "Number of Vials Used" recorded on Treatment Kit Accountability Log}) + 1$$

The adjustment of +1 will be applied to subjects who have Day 90 in-office dosing completed after the Treatment Kit Accountability Log for Day 60 kits are recorded.

The number of expected doses is calculated as the following:

$$2 \times (\text{Date of Last Dose} - \text{Date of First Dose}) + 1$$

for all subjects, regardless of study completion status. The adjustment of +1 is because there will be only one "evening" dose on the day of the first dose and two doses are expected for all other days till study exit. The date of last dose is the latest non-missing dosing date collected on the Study Drug Administration eCRF page or the Study Exit eCRF page, and the date of first dose is collected on the Study Drug Administration eCRF page.

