14.2 Clinical Laboratory Data

Clinical laboratory data including hematology, coagulation, and urinalysis will be collected at Baseline (Day 1), and Day 90 or ET. Overall clinical laboratory results at each visit will be reviewed and be interpreted as normal, abnormal, NCS (non-clinically significant), and abnormal, CS (clinically significant). Abnormal, CS results will be specified.

The actual and change from baseline in laboratory test results will be summarized using continuous descriptive statistics for each treatment group. The interpretation of results relative to the reference range (low panic, low normal, normal, high normal, high panic, abnormal) will be summarized using counts and percentages for each treatment group. Shift tables for the interpretation of results relative to the reference range will be provided comparing baseline with Day 90.

Subject listings of laboratory results (hematology, coagulation, and urinalysis) will be produced. When deemed necessary, manual differential results may be collected, which will be listed in the subject listing for hematology. Urine microscopic results may be collected when abnormal urinalysis results are observed,

which will be listed in the subject listing for urinalysis. In addition, the overall laboratory results review and interpretation at each visit will be presented in a separate listing.

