14.3 Vital Signs

Vital signs (sitting heart rate in beats/min and sitting blood pressure in mmHg [systolic and diastolic blood pressure]) will be assessed at Screening, Baseline (Day 1), and Day 90 or ET.

The actual and change from baseline in vital signs will be summarized using continuous descriptive statistics by visit for each treatment group. A subject listing of vital signs will be produced.

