14.6 Intraocular Pressure

Intraocular pressure will be assessed in both eyes at Screening, Baseline (Day 1), Day 90 and ET by a Goldmann applanation tonometer affixed to a slit lamp as preferred device. Results will be taken from a single measurement and will be recorded in mmHg.

The IOP values and changes from baseline for each eye (study eye and fellow eye) will be summarized using continuous descriptive statistics by visit and for each treatment group. A subject listing of IOP will also be produced.

[figure not shown]

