14.7 Dilated Fundus Exam

Dilated fundus exam of vitreous, retina, macula, optic nerve, and choroid will be performed at Screening, Baseline (Day 1), and Day 90 or ET. The results will be graded as normal, abnormal NCS, or abnormal CS.

Shift tables for the dilated fundoscopy parameters will also be provided comparing each follow-up visit to baseline by region, finding, and eye (study eye and fellow eye). A subject listing of the dilated fundoscopy parameters will also be produced.

15. Interim Analyses

No interim analysis is planned for the study.

17. References

1. *ICH Harmonised Tripartite Guideline: Statistical Principles for Clinical Trials E9*. International Council for Harmonisation of Technical Requirements for Pharmaceuticals for Human Use. 05 February 1998.
2. *ICH Harmonised Tripartite Guideline: Addendum on Estimands and Sensitivity Analysis in Clinical Trials to the Guideline on Statistical Principles for Clinical Trials E9(R1)*. International Council for Harmonisation of Technical Requirements for Pharmaceuticals for Human Use. 20 November 2019.
3. *ICH Harmonised Tripartite Guideline: Structure and Content of Clinical Study Reports E3*. International Council for Harmonisation of Technical Requirements for Pharmaceuticals for Human Use. 30 November 1995.
5. *PharmaSUG-2013-SP03: Combining Analysis Results from Multiply Imputed Categorical Data*.

19. Tables

Tables that will be included in the topline delivery are shown in boldface font. The topline will be delivered in two batches. Batch 1 tables are shown in boldface font and batch 2 tables are in boldface and italic font.

Table Number	Title	Population
Table 14.1.1	Subject Disposition	All Subjects
Table 14.1.2.1	Demographics and Baseline Characteristics	Intent-to-Treat Population
Table 14.1.2.2	Demographics and Baseline Characteristics	Safety Population
Table 14.1.3.1	Ocular Medical History	Safety Population
Table 14.1.3.2	Non-Ocular Medical History	Safety Population
Table 14.1.4.1	Ocular Concomitant Medications	Safety Population
Table 14.1.4.2	Non-Ocular Concomitant Medications	Safety Population
Table 14.1.5.1	Dosing Compliance	Safety Population
Table 14.1.5.2	Treatment Exposure Duration	Safety Population

Table Number	Title	Population

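### SAP 8.5 leaves early-termination values in listings only, so tabulated post-baseline labs, vital signs, IOP and fundus results cover only subjects with a Day 90 visit; slit lamp also lacks a worst-value summary

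*SAP*

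**What the plan says.** SAP 8.5 (Data Analysis Conventions) sets a general display rule: "Early termination visit (ET) and unscheduled visits will not be summarized in table summaries and will only be presented in listings". That sentence carries no exception of its own.

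Four safety measures have a single scheduled visit after Baseline:

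- **Laboratory tests.** In the schedule of SAP 3.2 (Table 1), the row "Hematology, chemistry, and urinalysis" is marked at Baseline, Day 90 and ET only. SAP 14.2 adds: "Shift tables for the interpretation of results relative to the reference range will be provided comparing baseline with Day 90".
- **Vital signs** (SAP 14.3): "will be assessed at Screening, Baseline (Day 1), and Day 90 or ET".
- **IOP** (SAP 14.6): "Intraocular pressure will be assessed in both eyes at Screening, Baseline (Day 1), Day 90 and ET".
- **Dilated fundus exam** (SAP 14.7): "will be performed at Screening, Baseline (Day 1), and Day 90 or ET". Shifts are planned for each follow-up visit.

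SAP 7.3 states: "The Safety population will be analyzed for all safety assessments". The table list in SAP 19 labels the tables for all four measures Safety Population. Protocol 7.3 lists the same four measures among the ET procedures and tells sites to try hard to perform them. Protocol 6.10.1 repeats this for subjects who withdraw consent or are discontinued for non-compliance.

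On worst values, Protocol 9.11 plans a summary of change from Baseline to the worst on-treatment value for ocular safety assessments. SAP 14.4 provides this for visual acuity, taking the maximum over scheduled or unscheduled post-baseline visits. SAP 14.5 gives slit lamp a shift table for each follow-up visit and nothing across visits. SAP 14.6 and 14.7 have no worst-value summary.

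**The concern.** A subject who leaves before Day 90 can contribute a post-baseline laboratory, vital-sign, IOP or fundus value at the ET visit, and not at any other scheduled visit. If ET values go only to listings, that subject contributes nothing to the post-baseline rows or shifts for these measures. The table still carries the Safety Population label, but its content is what was seen in people who reached Day 90. Subjects who stop early may differ in tolerability, so this is the group a safety reader would want included. The trial plans to collect these values and then does not tabulate them by arm.

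The slit-lamp issue is separate. Slit lamp has four scheduled post-baseline visits (Days 7, 14, 28 and 90), so leavers do appear in the rows up to the time they left. But shift counts at each visit do not give the number of different subjects who worsened at any time, which is what a worst-value summary supplies.

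What is at stake is the completeness of descriptive safety tables. Nothing here touches the efficacy analyses, the type I error or the power.

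**Working it through.** **Inputs.** About 460 randomized, 230 per arm, 10% dropout (Protocol 9.7, SAP 5). About 414 expected to complete Day 90 (Protocol 4.1). I take every randomized subject to be dosed, so that the Safety population is also 460, and every completer to have a Day 90 value. ET attendance, written *a*, is given nowhere; it is an assumption and I show its whole range.

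**The plan's own figure.** 460 × (1 − 0.10) = 414. This reproduces Protocol 4.1 exactly.

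**Subjects without a Day 90 value.** 460 − 414 = 46, or 46 / 2 = 23 per arm. The Day 90 rows would hold 414 / 460 = 90.0% of subjects, 207 per arm.

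**How much of this comes from SAP 8.5.** Only leavers who attend ET have a value that the rule removes. That number is 46 × *a*. Coverage with an added row for Day 90 or ET is (414 + 46*a*) / 460.

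| Assumed ET attendance *a* | Values removed by 8.5 | Coverage with added row |
|---|---|---|
| 0 | 0 | 90.0% |
| 0.50 | 23 | 95.0% |
| 1.00 | 46 | 100% |

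**Effect on a shift rate (illustration with assumed rates).** Suppose 2% of completers and 10% of ET attendees shift to abnormal. Per arm the rate with ET included is (207 × 0.02 + 23*a* × 0.10) / (207 + 23*a*).

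- *a* = 0.50: (4.14 + 1.15) / 218.5 = 2.42%.
- *a* = 1.00: (4.14 + 2.30) / 230 = 2.80%.

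The Day 90 row alone shows 2.0%. If the two groups have equal rates, nothing changes.

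**Slit lamp (illustration).** Suppose 5 subjects in an arm are worse than Baseline at each of the four visits. If they are the same people, 5 subjects ever worsened: 5 / 230 = 2.2%. If they are all different, 4 × 5 = 20: 20 / 230 = 8.7%. The by-visit tables look the same in both cases.

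**Where a worst-value summary would add something.** For IOP and fundus the only scheduled post-baseline value is Day 90, so on scheduled data the worst value is the Day 90 value. Among the ocular measures without such a summary, only slit lamp loses information on scheduled data.

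**Could a table be hidden by redaction?** In the SAP table list the numbers run 14.3.5.1, 14.3.5.2 (slit lamp), 14.3.6 (IOP) without a gap, which argues against a blacked-out slit-lamp table.

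**The case against.** The strongest reply is that this is a display choice, stated in advance. SAP 14.2 openly compares Baseline with Day 90, in agreement with 8.5. A row of observed values at one time point is a legitimate descriptive summary, and ET values come at mixed exposure, some after the last dose: the schedule marks no in-office dose at ET. This stands as a reason to leave the Day 90 row as it is and to label any added row separately. It is not a reason to tabulate the ET values nowhere.

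A reader might infer that early leavers disappear from all tables. They do not. Disposition is shown by arm with reasons (SAP 9). Compliance is computed "starting from Baseline (Day 1) to Day 90 (or ET) will be assessed by" a ratio (SAP 12.1), and exposure runs to the last dose (SAP 12.2). Adverse event tables are event-based and include events leading to discontinuation (SAP 14.1). Protocol 6.9.7 turns clinically significant laboratory changes at exit into adverse events. What is lost is only the measured values and shifts of ET attendees. Nor does the compliance formula show that this SAP pools ET with Day 90 measurements: there, ET only marks the end of the subject's own dosing period.

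A reader might also infer an undocumented departure from the protocol. The documents do not support that. SAP 1 says that its methods supersede the protocol's, and parts of the SAP (Section 8.6, Section 16 and text next to 8.5) are not visible, so an explanation or a visit-mapping rule cannot be excluded. It can also be argued that the worst-value sentence in Protocol 9.11 speaks of changes, which fits numeric measures better than graded slit-lamp findings. That makes the slit-lamp gap arguable, not a clear breach.

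Finally, SAP 14.4 might be read as contradicting 8.5 because it uses unscheduled visits. A derived maximum per subject is a specific rule and can stand beside a general one. Only a clarification is needed.

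**Conclusion.** The point holds as a minor one. On the visible text, tabulated post-baseline results for laboratory tests, vital signs, IOP and fundus describe subjects with a Day 90 visit, not the whole Safety population named in the table titles. At the planned dropout, 46 subjects would be missing from those rows. It would be wrong to attribute all 46 to SAP 8.5: leavers who never attend ET have no value to recover. The loss due to the rule lies between 0 and 46, and the documents do not narrow it. Any effect on a reported rate depends on assumed differences between leavers and completers, and in the illustration above it is under one percentage point.

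For slit lamp, the visible plan gives no count of subjects who ever worsened, although Protocol 9.11 can be read as asking for a worst on-treatment summary. Confidence is medium, mainly because parts of the SAP are not visible.

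**What to change.** **(a) ET values.** In SAP 8.5, limit the exclusion to by-visit rows and say that ET values enter the last-assessment summaries named in Section 14. In 14.2, 14.3, 14.6 and 14.7, keep the Day 90 row and add a separately labelled row, 'Last assessment (Day 90 or ET)', with the matching shift where shifts are planned (14.2 and 14.7). Show how many values come from each visit and, for ET values, the days since last dose, using the last-dose date already defined in 12.2.

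**(b) Slit lamp.** In SAP 14.5, add a worst-value shift and name it for what it counts: 'worst on-treatment' if restricted to on-treatment values, as in Protocol 9.11, or 'worst post-baseline' if ET or other off-treatment values are included. State in 8.5 that it is an exception if it uses ET or unscheduled values.

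**(c) Optional clarification.** In SAP 14.4, say whether ET values enter the maximum, and that this summary is an exception to 8.5.

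**Cost.** Some SAP wording and a few table rows, from data already planned for collection; trial conduct does not change. The downside is that ET values come at varying exposure, some after the last dose, which is why the separate label and the days since last dose are needed. If the sponsor prefers Day 90 only, the SAP should say so and give the reason, including for slit lamp.
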